There also exists an extensive history of using MDMA as an adjunct to psychotherapy prior to scheduling (Adamson 1985; Greer and Tolbert 1986; Greer and Tolbert 1998; Grinspoon and Bakalar 1986; Metzner and Adamson 2001; Stolaroff 2004; Widmer 1998). Narrative accounts and case reports of MDMA given in these circumstances indicated that MDMA was tolerated and that no serious adverse events occurred. Two uncontrolled studies of MDMA (Downing 1986; Greer and Tolbert 1986), including one performed in a psychotherapeutic context (Greer and Tolbert 1986) also found that participants tolerated MDMA and reported no serious adverse events. Lastly, during a period lasting from 1988 to 1993, psychotherapists in Switzerland were permitted to administer

MDMA to patients (Gasser 1994; Widmer 1998). These therapists reported that MDMA-assisted psychotherapy was tolerated and did not report any serious adverse events occurring after MDMA administration.

In summary, researchers have measured the cardiovascular, physiological, neuroendocrine, neurofunctional (PET and EEG), psychiatric, and subjective effects of MDMA at doses ranging from 0.25 to 2.5 mg/kg, and are currently studying the effects of 125 mg MDMA given as an adjunct to psychotherapy in people with PTSD. MDMA has been generally well tolerated in these studies, and we are aware of no drug-related serious adverse events. Participants with and without previous experience with MDMA reported that the effects of MDMA were mostly pleasant and otherwise tolerable (Cami et al. 2000; Farre et al. 2004; Grob et al. 1996; Harris et al. 2002; Hernandez-Lopez et al. 2002; Liechti et al. 2001; Tancer and Johanson 2001; Tancer and Johanson 2003; Vollenweider, 1998). Occasionally, dysphoric responses to MDMA have occurred, but have always resolved within several hours, and transient changes in thought processes are reported (Harris et al. 1998; Vollenweider et al. 1998). Clinically significant hypertension has occurred in several volunteers; these cases are discussed above. To date, there is no indication that administration of MDMA in controlled settings has any adverse effects on cognitive function (Grob et al. Unpublished; Ludewig et al. 2003; Vollenweider et al. 2000). Grob et al. did not detect any change in neurocognitive function in their volunteers. Similarly, Vollenweider and colleagues (Ludewig et al. 2003; Vollenweider 2001; IND #63,384 pp. 189-190; Vollenweider et al. 2000) report that retrospective analysis of their studies did not detect any lasting effect of MDMA on psychological and neuropsychological measures, cerebral blood flow ($H_2^{15}O$ -PET), and electrophysiological indices of information processing such as prepulse inhibition of the startle reflex (PPI) and brain wave activity (EEG/ERP). Most importantly, preliminary analysis using positron emission tomography (PET) and the radioligand McN-5256 revealed no significant changes in estimated serotonin transporter density four weeks after a single dose of MDMA (1.5–1.7 mg/kg) in MDMA-naïve volunteers (Vollenweider et al. 2001). This data and the history of past use of MDMA in psychotherapy prior to scheduling indicate that MDMA can be safely administered to humans.

6. Drug Dependence and Abuse Liability

MDMA is classified as a Schedule I compound (in Switzerland “Betäubungsmittel”) with a high potential for abuse, primarily because of its use in settings such as “rave” or dance parties. Whether or not MDMA’s abuse potential will negatively affect PTSD patients exposed to MDMA in a therapeutic context is an open question for which there is no direct data. However, instead of experiencing euphoria, people with PTSD undergoing MDMA-assisted psychotherapy are likely to experience painful and frightening emotions and memories related to the original traumatic incident. During MDMA-assisted therapy, they are expressly directed to confront and process emotionally intense, and often upsetting, material. As a result, it seems unlikely that people with PTSD undergoing this emotionally challenging psychotherapy will find the experience pleasurable or safe enough to pursue MDMA use in unsupervised and uncontrolled settings.

In the currently proposed study, diversion is not an issue because MDMA will only be administered under supervision of a research psychiatrist and no take-home doses will be permitted.

Recreational use of MDMA first appeared possibly as early as the 1960s (see Shulgin 1991) and is known to have occurred during the late 1970s and early 1980s. Instances of abuse and dependence in users have been reported (Jansen 1995; Topp et al. 1999). While studies using non-representative samples, including samples of drug users, have reported diagnosing up to 30% of users with abuse or dependence (Topp et al. 1999 Cottler et al. 2001), a survey of a representative sample of young Munich residents found that 6% of people reporting ecstasy use had signs of abuse or dependence on the drug. This suggests that some people who take ecstasy may develop substance abuse or dependence. Several studies have found that in general, people begin using ecstasy only after they

have begun using cannabis or other illicit substances (Pedersen and Skrondal 1999; see also age of onset in Daumann et al. 2004, for example). Measuring reward value by finding the point at which people would switch from receiving drug to either giving up or receiving money, Tancer and Johanson (2003) found that 2 mg/kg MDMA and 20 mg d-amphetamine had higher reward value than placebo, and that 1 mg/kg MDMA and 10 mg d-amphetamine did not have significantly higher reward value than placebo. Participants in this study were selected for past use of ecstasy and minimal use of other substances, so it seems likely that participants in this study would assign high reward value to MDMA.

Studies in rodents (e.g. Cornish et al. 2003; Robledo et al. 2004; Schenk et al. 2003; Wakonigg et al. 2004) and non-human primates (Beardsley et al. 1986; Fantegrossi et al. 2002; Fantegrossi et al. 2004; Lamb and Griffith 1987; Lile et al. 2005) suggest that animals will self-administer MDMA. Conditioned place preference, referring to the tendency to spend more time in a chamber associated with an injection of the drug, was reported to occur in rats given MDMA (Bilsky et al. 1990; Cole and Sumnall 2003; Meyer et al. 2002). A study that examined the rapidity with which a drug-naïve rat descended a runway to obtain an injection of MDMA also found that descent was more rapid when MDMA was available (Wakonigg et al. 2004). All of these findings suggest that MDMA possesses some reward value for rats, usually considered a sign of human abuse potential.

A number of studies have found that non-human primates self-administer MDMA, though to date, all studies have employed animals previously experienced with the self-administration of other substances, such as cocaine or methamphetamine, either previous to the study or with cocaine offered before MDMA. Rhesus monkeys self-administered an average of 2 to 4 mg/kg MDMA in one study (Fantegrossi et al. 2004) during twice-daily hour-long sessions occurring approximately three times a week. Less self-administration was seen at the end of an eighteen-month period, suggesting that when repeatedly self-administered, MDMA loses some reward incentive. Rhesus monkeys were willing to work to self-administer MDMA, but they were willing to work harder to self-administer cocaine (Lile et al. 2005). Overall findings in non-human primates support the presence of at least some abuse liability. Baboons that had previously self-administered cocaine also self-administered MDMA (Beardsley et al. 1987).

Drug-naïve participants without any major psychiatric illnesses who were taking part in clinical trials of 1.5 to 1.7 mg/kg MDMA conducted in a non-psychotherapeutic setting reported that they had no interest in self-administering the drug outside the confines of a controlled laboratory setting (Liechti et al. 2001).

There is known to be significant comorbidity for substance abuse among patients with PTSD, though specific data on the relationship between MDMA use and PTSD have not been reported. Currently, there is no definite evidence concerning the causal relations between the two disorders, and it is unclear whether posttraumatic stress disorder precipitates substance abuse or whether people with pre-existing substance abuse are at greater risk for PTSD. Currently, the most commonly accepted hypothesis for the relationship between PTSD and substance abuse is that of self-medication (Meisler, 1996). Since individuals undergoing the proposed treatment will be encouraged to confront the traumatic events during MDMA-assisted therapy rather than defending against them or avoiding them, it seems likely that these individuals will subsequently be less inclined to choose to self-medicate through the self-administration of MDMA. If our hypothesis is correct that MDMA assisted psychotherapy will alleviate symptoms of PTSD, then participants will be at reduced risk for substance abuse in general following MDMA-assisted psychotherapy because they will have a reduced motivation to self-medicate. There will be no opportunity for diversion in this study because all doses of MDMA will be administered within the clinic, and there will be no take-home doses.

7. References

Adamson S (1985) Through the Gateway of the Heart: Accounts of Experiences with MDMA and Other Empathogenic Substances. San Francisco: Four Trees Publications.

Aghajanian GK, Lieberman JA (2001) Response. *Neuropsychopharmacology* 24: 335-336.

Alting Von Geusau N, Stalenhoef, P, Huizinga M, Snel J, Ridderinkhof KR (2004) Impaired executive function in male MDMA (Ecstasy) users. *Psychopharmacology (Berl)*, Published online March 18, 2004. DOI: 10.1007/s00213-004-1832-1838.

American Psychiatric Association (1994) *Diagnostic and Statistical Manual of Mental Disorders (DSM-IV)*. Washington DC: American Psychiatric Association Press.

Baggott M (2002) Preventing problems in ecstasy users; Reduce use to reduce harm. *J Psychoactive Drugs* 34:145-162.

1.0 Definitions

Categorical data: This refers to discrete (indivisible) variables, such as gender or ethnicity. These data will be presented as total numbers of each category as needed to describe the sample.

Descriptive data: This includes mean, median, standard deviation, minimum and maximum of numerical data used as needed to describe the sample.

Difference scores: These consist of scores computed by subtracting one value from another, as subtracting baseline from End of Stage 1 score, used to test for differences between and within groups to determine change as a function of experimental treatment over time.

Efficacy: A type of analysis used to assess therapeutic effects or benefits.

Exploratory analyses: An inferential or descriptive analysis of the data to determine trends that might lead to hypotheses for further study.

Frequency listing: A tabular listing of numbers and/or percentages of events used as needed to describe the sample or data characteristics.

Outcome measures: These are primary and secondary study measures that are used to test the study hypotheses.

Process measures: These are study measures or qualitative observations collected during the study that may increase depth of understanding and that are not necessarily related to safety or efficacy.

Protocol deviation: An event that represents significant divergence from the intended study design as described in the protocol.

Safety: An assessment of the condition of study subjects that examines potential risks, adverse events and reactions.

Safety measures: These are study measures that assess safety, such as blood pressure monitoring. These measures are used to assess safety of the study drug.

Study design: All elements of a research project that define the study question, experimental methods, study procedures including blinding and randomization, measurement techniques, flow sheet of data, and statistical analysis.

Tabular Listing: A list of each variable or item for each individual subject either in total or by condition in a table format.

2.0 Introduction

This is a data analysis plan for the study “3,4-methylenedioxymethamphetamine-assisted psychotherapy in Twelve Patients with Treatment-Resistant Posttraumatic Stress Disorder (PTSD.”

3.0 Study Objectives

As stated in the protocol, the following main questions are to be explored in the proposed study:

1. Can MDMA, in the doses to be used in this study, be safely administered in the population of treatment-resistant PTSD patients without any serious adverse events?
2. Will patients receiving the larger, fully active dose of MDMA, in combination with non-drug assisted psychotherapy, demonstrate greater symptomatic improvement than patients given an active placebo dose of MDMA in combination with non-drug psychotherapy?
3. Will patients receiving three MDMA sessions in combination with non-drug psychotherapy demonstrate an additional improvement compared to patients receiving only two sessions?
4. Can treatment effects of MDMA-assisted psychotherapy be maintained beyond end of treatment?

3.1 Primary Objective

To evaluate changes in PTSD symptoms via CAPS scores gathered at baseline, three weeks after the second experimental session, and three weeks after the third experimental session.

3.2 Secondary Objectives

- To evaluate changes in PTSD symptoms as assessed via PDS at baseline, the day after each experimental session, and three weeks after the third experimental session.
- To evaluate PTSD symptoms measured by CAPS and PDS scores three weeks after the second Stage 2 experimental session, three weeks after the third Stage 2 experimental session and two months after the third Stage 2 experimental session.
- To formally or informally evaluate CAPS scores in participants who underwent an optional open label continuation for treatment non-responders (Stage 3).
- To evaluate changes in PTSD symptoms assessed via CAPS and PDS scores obtained two, six and twelve months after the third experimental session.

3.3 Safety Objectives

The safety objective presented in the protocol is item 1 in the Study Objectives listed above and has been formulated as individual objectives below:

- To assess blood pressure and pulse during experimental sessions using automated blood pressure and pulse monitoring equipment.
- To assess body temperature at regular intervals during experimental sessions.
- To assess experience of degree of psychological distress by repeated administration of the Subjective Units of Distress (SUD) during experimental sessions.

4.0 Study design

The study followed a randomized, active placebo-controlled, double-blind design, with subjects, psychotherapists and independent raters blinded to participant condition. Twelve subjects with treatment-resistant PTSD were randomly assigned after baseline assessment to receive either full dose of 125 mg MDMA followed by a supplemental dose of 62.5 mg MDMA administered 2.5 h

later, or to an active placebo dose of 25 mg MDMA followed by 12.5mg MDMA 2.5h later. Participants underwent three sessions of MDMA-assisted psychotherapy scheduled to occur three to five weeks apart, 1 non-drug-psychotherapy session 24 h after each MDMA-session and 2-4 weekly integrative psychotherapy sessions after each MDMA session. PTSD symptoms were assessed by an independent rater once prior to MDMA-assisted psychotherapy, three weeks after the second MDMA-assisted session, three weeks after the third experimental session. After unblinding, active placebo participants had the opportunity to take part in an open-label continuation of the study, referred to here as "Stage 2." Data gathered three weeks after the third experimental session was treated as the baseline for Stage 2, and outcome measures were administered three weeks after the second and third experimental session. Originally outcome measures would also be given two, six and twelve months after the third experimental session, but the six-month evaluations were discontinued after January 2009 in line with the Amendment 5 of the protocol. Participants receiving the full dose in either Stage 1 or Stage 2 who did not show significant improvement in PTSD symptoms were offered the opportunity to take part in an open-label continuation of the study, "Stage 3", consisting of two additional MDMA sessions. During these sessions, they could receive 125 mg followed 2.5 hours later by 62.5 mg MDMA or a 20% larger dose of 150 mg MDMA, followed by a supplemental dose of 75 mg administered 2.5 hours later, unless contraindicated by safety parameters. Outcome measurements gathered at 2 months after the third experimental session will serve as baseline measures for Stage 3. Stage 3 was also cancelled in line with Amendment 5. Of the 12 participants who completed the study, only three participants underwent Stage 3.

4.1 Time and Events table

Please see attached document.

5.0 Measures

5.1 Outcome Measures

- Clinician-Administered PTSD Scale (CAPS) Global Score, subscale scores (B, C, D, F), Diagnostic criteria Met score, Associated Features (#26, 27, 28, 29, 30)
- PTSD Diagnostic Scale (PDS) Score, Rating, Impairment

5.2 Safety Measures

- Subjective Units of Distress (SUD)
- Vital signs (Systolic blood pressure (SBP), diastolic blood pressure (DBP), heart rate (HR), body temperature (BT))
- Spontaneously reported reactions during experimental sessions and seven days afterward
- Adverse events reported during the study
- General well-being assessment

5.3 Process Measures

Reactions to Research Participation Questionnaire – Short Form Revised (RRPQ)
Subject Belief of Condition Assignment

6.0 Analyses

6.1 Study population

See protocol. All participants were diagnosed with chronic PTSD, met DSM IV criteria, and had Global CAPS scores of 50 or greater upon enrollment. They had either undergone psychotherapy, pharmacotherapy or both without a significant reduction in PTSD symptoms.

All clinical data will be presented in tabular listings. All analyses will be carried out with SPSS of Version 12.0 or higher.

Definitions of subject populations for analysis:

All Enrolled: All participants who signed an informed consent form and completed baseline measures.

Intention to treat: All participants who were randomized to a condition and underwent at least one experimental session. All available data will be used.

Per Protocol: All participants who completed Stage 1 and underwent assessment of PTSD symptoms two months after the second experimental session. Analyses may be conducted with and without a participant who corresponds to a major protocol deviation.

Partial crossover: All participants who completed Stage 2 as well as Stage 1.

Extended Assessment 1: All participants who underwent assessment two, six and twelve months after their third Stage 1 or Stage 2 experimental session.

Extended Assessment 2: All participants who underwent Stage 3

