2.7. Participants

The first twelve participants who meet all inclusion criteria without meeting any exclusion criteria will be admitted to the study. Participants enrolled in the study who withdraw during treatment or who the researchers decide for any reason should not continue in the study (“drop-outs”) will be replaced. Participants will be recruited for the study by call for referral from specialized institutions such as trauma advice and counseling centers (outpatient clinics for psychotraumatology), as well as psychiatrists and psychotherapists in private practice (see enclosed).

2.7.1. *Inclusion Criteria*

Participants who meet the following criteria will be considered for inclusion in this study:

1. Participants must meet DSM IV criteria for current PTSD (within the past 6 months) in response to a traumatic experience. An individual would not be excluded if she or he experienced more than one traumatic event. Participants must have a CAPS score of 50 or higher, indicating moderate to severe PTSD symptoms.
2. They must have had at least one unsuccessful attempt at treatment for PTSD. Treatments include psychotherapy and pharmacotherapy. Pharmacotherapies may include selective serotonin uptake inhibitors (SSRIs). Psychotherapeutic treatments may include, but are not limited to cognitive-behavioral therapy (including exposure therapy), stress inoculation training, including anxiety management, and insight-oriented psychotherapy (Foa et al. 2003; Jaycox et al. 2002; Krupnik 2002; Resick and Schnicke 1992). Treatment will be deemed unsuccessful if the participant continues to meet criteria for current PTSD following the treatment.
3. Participants may also meet criteria for a mood disorder (except bipolar affective disorder, see exclusions) and for other anxiety disorders. The inclusion of people with other mood and anxiety disorders is essential because recent literature (Brady et al., 1994; Faustman & White, 1989) indicates the marked frequency of the co-existence of other psychiatric disorders among patients with PTSD.
4. Participants must be at least 18 years old.
5. Participants must be willing to commit to medication dosing, therapy sessions, and follow-up sessions and to complete evaluation instruments.

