2.8.2. Assessments and Measures

Psychiatric diagnoses will be made through the Structured Clinical Interview for Diagnoses (SCID), and PTSD symptoms will be measured by the Clinician Administered PTSD Scale (CAPS) during screening to determine whether an individual may participate in the study.

PTSD symptoms will be assessed six times in this study:

- T0: *Baseline assessment*
- T1: *Post MDMA 2 assessment*: 3 weeks after the second experimental session (MDMA 2)
- T2: *End of treatment assessment*: 3 weeks after the third experimental session (MDMA 3)
- T3: *1st follow-up assessment*: 2 months after the third experimental session (MDMA 3)

T4: *2nd follow-up assessment*: 6 months after the third experimental session (MDMA 3) for all participants assigned to the Fully Active Dose condition, and all participants assigned to the Low Dose condition who choose not to take part in the open-label study continuation.

T5: *3rd follow-up assessment*: 12 months after the third experimental session (MDMA 3) for all participants assigned to the Fully Active Dose condition, and all participants assigned to the Low Dose condition who choose not to take part in the open-label study continuation.

Participants who choose to take part in the open label study continuation “Stage 2” will be assessed identically to stage 1 three weeks after the second and third (end of treatment) experimental sessions and two, six and twelve months after the third experimental session in Stage 2. The T2 assessment will serve as baseline for stage 2.

Participants who choose to take part in the open label study continuation “Stage 3” will be assessed identically to stage 1 three weeks after the second (end of treatment) experimental session and two, six and twelve months after the experimental session in Stage 2. The T3 assessment will serve as baseline for stage 3.

All outcome measures will be administered by an independent assessor. The independent assessor will remain blind to subject condition and will not be present during psychotherapy sessions. The CAPS will serve as the primary outcome measure, and the PDS will serve as additional measure of PTSD symptoms. The CAPS and the PDS are specifically designed to assess PTSD. German versions of all measures will be used in this study.

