6.4.1 Main analyses

Goal: To determine if there is a main effect of condition on PTSD symptoms and criteria for meeting PTSD, three weeks after the second experimental session and three weeks after the third experimental session 1.

Population: Intention to Treat and Per protocol

Data included in analyses: CAPS (Global Score, subscales, and Diagnostic criteria met)

Format of analyses: Repeated-measures ANOVA. If multiple scores from a single scale are assessed, Bonferroni corrections were applied.

Time: Baseline, 3 weeks after Exp. Session 2, 3 weeks after Exp. Session 3

Between-groups factors: Condition (125 mg MDMA, 25 mg MDMA)

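### The SAP promises all available data for intention to treat, but the only method it names for the main CAPS analysis, in its classical form, drops any participant missing one of three visits

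*SAP*

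**What the plan says.** SAP 6.1 sets both the membership of the set and the data it will use: "Intention to treat: All participants who were randomized to a condition and underwent at least one experimental session. All available data will be used".

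SAP 6.4.1, the main efficacy analysis, applies one method to two sets:

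- "Population: Intention to Treat and Per protocol"
- "Format of analyses: Repeated-measures ANOVA"
- "Time: Baseline, 3 weeks after Exp. Session 2, 3 weeks after Exp. Session 3"

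On software, SAP 6.1 says only this: "All analyses will be carried out with SPSS of Version 12.0 or higher". It names no procedure.

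Protocol 2.7 provides for replacing participants "who withdraw during treatment or who the researchers decide for any reason should not continue in the study". Neither document describes assessing them after they leave. Neither gives a rule for missing CAPS or PDS values: there is no imputation, carry-forward, mixed model or missing-data sensitivity analysis.

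Protocol 2.8.2 places the first post-baseline CAPS (T1) three weeks after the second experimental session and the end-of-treatment CAPS (T2) three weeks after the third. Protocol 2.8.3 had planned a rank-based longitudinal model (F1_LD_F1) to compare the arms over time.

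**The concern.** A classical repeated-measures ANOVA on T0, T1 and T2 works on complete three-value records. A participant who had a session and then left, or who missed one assessment, is in the intention-to-treat set under SAP 6.1 but cannot enter that ANOVA. Once anyone is incomplete, the data promise and the named method cannot both be kept.

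The plan foresees incomplete participants. Protocol 2.7 expects drop-outs and replaces them, and Protocol 2.8.8 lists safety events after which no further experimental session is given. Such people may have left because of poor tolerability or poor response, and an intention-to-treat analysis exists to keep them. If they drop out of the calculation without notice, a result labelled intention to treat carries the selection of a complete-case analysis. With four participants planned in the low-dose arm, each lost record also counts for a good deal.

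**Working it through.** The documents give no power figure, effect size, SD or drop-out rate, so there is no plan figure to reproduce. The checks below show what the named method would do under stated assumptions.

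**Inputs**

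- Allocation 8 full dose, 4 low dose (Protocol 2.8.1): 8/12 = 66.7%, 4/12 = 33.3%.
- Three CAPS visits in the main analysis (SAP 6.4.1).
- Twelve completers (SAP 4.0).
- Significance level 0.05 (Protocol 2.8.3). Sidedness is not stated; two-sided is assumed.
- Number of drop-outs k and missed-visit rate p: not given, so a range is shown.

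**Step 1. Drop-outs who are replaced.** Suppose 12 participants complete all three visits and k others had at least one session, left and were replaced. The intention-to-treat set is 12 + k. The complete-case ANOVA still has 12. Share omitted = k/(12 + k).

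| k (assumed) | Intention-to-treat set | In the ANOVA | Omitted |
|---|---|---|---|
| 0 | 12 | 12 | 0% |
| 1 | 13 | 12 | 7.7% |
| 2 | 14 | 12 | 14.3% |
| 3 | 15 | 12 | 20.0% |
| 4 | 16 | 12 | 25.0% |

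The number analysed does not fall in this case, so power is not lost. The harm is bias and a wrong label.

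**Step 2. A missed visit among the 12.** If each of the two post-baseline visits is missed independently with probability p (assumed), expected complete cases = 12(1 − p)², and the chance of losing at least one person = 1 − (1 − p)²⁴.

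| p (assumed) | Expected complete cases of 12 | Chance of at least one deletion |
|---|---|---|
| 5% | 10.8 | 71% |
| 10% | 9.7 | 92% |
| 20% | 7.7 | 99.5% |

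**Step 3. Power when one of the 12 is deleted and not replaced.** This is a two-sample t illustration, not the planned three-visit test. Noncentrality = d / √(1/n₁ + 1/n₂), with n₁ + n₂ − 2 degrees of freedom. For 8 v 4, √(1/8 + 1/4) = 0.612, so d = 1.9 gives 1.9/0.612 = 3.10 on 10 df. For 8 v 3, √(1/8 + 1/3) = 0.677, giving 2.81 on 9 df.

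| Arms | Detectable difference, 80% power | Power at 1.9 SD |
|---|---|---|
| 8 v 4 | 1.90 SD | 0.798 |
| 7 v 4 | 1.97 SD | 0.770 |
| 8 v 3 | 2.13 SD | 0.705 |
| 7 v 3 | 2.21 SD | 0.675 |

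**Step 4. What a mixed model recovers.** Take 12 completers, one person with T0 and T1 only, and one who left after the first session. The set is 14 and the complete-case ANOVA uses 12. A likelihood-based mixed model uses all 14, with 12 × 3 + 2 + 1 = 39 of 42 possible scores. Only 13 of the 14 have any post-baseline CAPS, because none is scheduled before T1. The person who left after session 1 contributes a baseline and no outcome.

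**The case against.** **The SAP never says incomplete cases are deleted.** This is correct. Deletion is the standard behaviour of the classical method; a mixed-model implementation would keep incomplete participants. But the SAP does not ask for one, and its statement on using all available data gives no means of doing so. The point therefore stands with deletion as a stated assumption.

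**Perhaps nobody was incomplete.** SAP 4.0 says twelve subjects were randomly assigned and refers to the 12 who completed. Read plainly, this means no drop-outs and, if no visit was missed, no effect on the result. That reading is possible but not conclusive. The sentence on assignment closely follows the design statement in Protocol 2.5, and with replacement under Protocol 2.7, reaching 12 completers is the intended end point however many were randomised.

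**A reader might infer that the intention-to-treat and per-protocol analyses become the same set.** The documents do not support that. SAP 6.2 allows participants with major deviations to be left out of per protocol while kept in intention to treat. SAP 6.1 also defines the per-protocol set by a further assessment: "Per Protocol: All participants who completed Stage 1 and underwent assessment of PTSD symptoms two months after the second experimental session". No visit is scheduled at that time; in Protocol 2.8.2 the two-month visit follows the third session. The exact overlap cannot be stated until that is clarified.

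**A reader might also infer that drop-out costs power.** For replaced drop-outs it does not: the analysis still has 12. The power figures apply only to an unreplaced missed visit, which no document reports, and they ignore the correlation between visits.

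**Conclusion.** The conflict between the data promise in SAP 6.1 and the method in SAP 6.4.1 is real and should be resolved. With classical repeated-measures ANOVA and no missing-data rule, the intention-to-treat result would leave out every participant lacking a T0, T1 or T2 CAPS.

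The size is conditional. With no incomplete participants it is nil. With 1 to 4 replaced drop-outs, 7.7% to 25% of the intention-to-treat set is omitted; the direction and amount of any bias cannot be worked out from the documents. If one low-dose participant among the 12 missed a visit, power at 1.9 SD would fall from 80% to about 70% in the two-sample illustration. All of this assumes classical ANOVA with deletion of incomplete cases; the power figures also assume a two-sided 0.05 test.

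The documents do not show that anyone was in fact lost.

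**What to change.** 1. In SAP 6.4.1, for the intention-to-treat set, replace repeated-measures ANOVA with a mixed model for repeated measures (condition, visit, condition by visit, small-sample degrees of freedom). The alternative is the rank-based longitudinal analysis of Protocol 2.8.3, implemented so that it accepts incomplete records. Name the procedure and state the missing-data assumption.
2. Keep the complete-case ANOVA as a sensitivity analysis, labelled as such.
3. Report the numbers randomised, replaced and analysed, by visit and arm. This alone would show whether the issue had any effect.
4. State that participants leaving before T1 have no post-baseline CAPS, so the model adds only their baseline. Specify an imputation sensitivity analysis for any inference that includes them.
5. Reconcile the assessment time in the per-protocol definition with the visit schedule.

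The cost is SAP wording and one further procedure; whether the stated software runs the chosen method should be checked. The mixed model assumes that data are missing at random, which cannot be verified here, and its estimation is somewhat fragile with about 12 participants. That is a reason to keep the simpler analysis beside it.
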